Once Aim 2 (above) is complete and 36 mentors have been trained, caregiver mentees will be matched with mentors by relationship to LBD patient, then by sex and age, as much as possible. Mentor and mentee preferences expressed in the mentoring preferences survey will be honored to the extent that the study team is able given the available mentor and mentee participants. The study team will contact mentees once a match is available for them. First, the study team will direct the mentee to complete baseline primary and secondary outcome assessments online via REDCap, including: mastery scale¹⁹, LBD knowledge test, loneliness scale⁴¹, Short Zarit Burden Interview (ZBI-12)⁴², Hospital Anxiety and Depression Scale (HADS)⁴³, Geriatric Depression Scale – Short Form (GDS-SF)⁴⁴, and Dementia Attitudes Scale (DAS)⁴⁵ in order to obtain their pre-intervention baseline. The study team will then provide the mentee with contact information for their mentor, and caregivers will be mailed the PERSEVERE handbook.

Mentor-mentee pairs will then begin the 16-week peer mentor program. During this time, pairs will be expected to speak for ≥15-30 minutes weekly, and to review that week's PERSEVERE topics in the handbook before or during each call to facilitate meaningful conversations. Discussions are not scripted and will not necessarily be limited to that week's topics, at the discretion of the participants. Mentors and mentees will complete online study diaries every 2 weeks, assessing intervention fidelity. Up to 3 email reminders will be sent and/or up to 3 phone calls attempted to complete each study diary. Diary entries will include information such as call frequency, duration, topics discussed, and concerns. At the Week 8 or Week 10 survey, all mentees and those mentors who are still actively caregiving for a loved one with LBD will complete the Parkinson's Disease Carer Questionnaire (PDQ-Carer), a novel measure of PD-specific caregiver quality of life. Mentors will participate in 4 recorded monthly conference calls to share successes, challenges, and feedback, and to ask questions of and be supported by the study team.

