Upon completion of the 16-week mentor program, mentors and mentees will be sent a link to complete postmentoring assessments online (mentors: mastery scale, LBD knowledge test, DAS, PDQ-Carer; mentees: mastery scale, LBD knowledge test, loneliness scale, ZBI-12, HADS, GDS-SF, DAS, PDQ-Carer, and fall frequency and healthcare utilization of their loved one; see Figure 3).

	Aim 2 - Mentor Training	Aim 3 – PERSEVERE Pilot
Primary	 Mastery scale¹⁹ 	Mastery scale
Outcomes	Multiple-choice LBD	 LBD knowledge test
	knowledge test	 Loneliness scale⁴¹
Secondary	Mastery Scale (after	 Short Zarit Burden Interview (ZBI-12)⁴²
Outcomes	mentoring)Dementia Attitudes Scale	 Hospital Anxiety and Depression Scale (HADS)⁴³
	 (DAS)⁴⁵ Parkinson's Disease Carer 	 Geriatric Depression Scale – Short Form (GDS- SF)⁴⁴
	Questionnaire (PDQ-Carer)	• DAS

Figure 3. Outcomes, Fidelity Metrics, Covariates, and Confounders in Aims 2 &

	(only if actively caregiving for loved one with LBD)	 Parkinson's Disease Carer Questionnaire (PDQ-Carer) 	
Fidelity Metrics		Frequency and duration of calls	
		 Number of missed calls/weeks 	
		 Coverage of target topics; other topics discussed 	
		Qualitative feedback in mentor conference	
		calls	
		 Dropout rate and reason 	
Demographics,	Sex, age, race, ethnicity, education, comorbidities, caregiving relationship, duration of		
Confounders,	caregiving; patient's disease duration, stage, ADLs ⁴⁶ and IADLs ⁴⁷ at baseline, and		
Covariates	patient's monthly frequency of falls and acute healthcare utilization (combined		
	number of ER visits not yielding admission + hospital nights) in the months prior to and		
	during the intervention.		

III.d. Assessments

All participants who agree to be part of the study and sign the informed consent form will be asked to complete a series of surveys and assessments. There is no known risk associated with completion of these assessments. All or some of the following measures may be administered but are not limited to:

- Mastery Scale: A 7-item scale measuring the extent to which a participant sees life as being under his/her personal control vs. something that is fatalistically ruled. Scores range from 7 to 28, with higher scores indicating greater levels of mastery.¹⁹

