- IV. Aim 3 (caregiver peer mentoring): We will analyze data fidelity by summarizing categorical variables by frequencies and percentages and will assess continuous variables for normality, summarized by mean/standard deviation or median/interquartile range. We will describe the baseline demographics, patient characteristics (including fall frequency and acute healthcare utilization), mastery, LBD knowledge, loneliness, ZBI, HADS, GDS-SF, and DAS of caregivers. Bivariate analyses will compare change between baseline and 16 weeks of mentoring in each of the above, using paired t-test or Wilcoxon sign rank, as appropriate. We will also compare change in PDQ-Carer between mid-study and Week 16 as an exploratory outcome. To examine potential covariate effects, we will run a series of repeated measures ANCOVAs for pre- and post- primary and secondary outcome measures using demographic and confounder variables as nuisance variables. These analyses will be considered exploratory due to the loss of degrees of freedom resulting from the covariates. Mentor program fidelity metrics including *dropout* rate and reasons, time spent on phone calls, number of phone calls, and topics discussed will be calculated

based on responses obtained from biweekly online study diary entries. Qualitative data will be gathered from the monthly mentor conference calls via notes taken by the study team; framework analysis will be applied to identify key themes regarding successes, challenges, and recommendations for improving the program.

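### PDQ-Carer is secondary in Figure 3 but exploratory in III.e, and with no mentee baseline the pilot cannot estimate whole-program change in carer quality of life

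*Combined protocol and SAP*

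**What the plan says.** The outcome table (Figure 3, section III.c) puts PDQ-Carer in the secondary outcomes row for Aim 3. The cell breaks across a page, but the entry sits above the fidelity metrics.

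Section III.c gives the timing for mentees:

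- Once a match is available, mentees complete mastery, LBD knowledge, loneliness, ZBI-12, HADS, GDS-SF and DAS "in order to obtain their pre-intervention baseline". PDQ-Carer is not in this list.
- The next step is "The study team will then provide the mentee with contact information for their mentor", so the survey falls before mentoring begins.
- PDQ-Carer first appears mid-program: "At the Week 8 or Week 10 survey, all mentees and those mentors who are still actively caregiving" for a loved one with LBD complete it.
- It appears again after the program, when the mentee list includes "ZBI-12, HADS, GDS-SF, DAS, PDQ-Carer, and fall frequency and healthcare utilization of their loved one".

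Section III.e, Aim 3, describes seven scales at baseline, without PDQ-Carer, and then states: "Bivariate analyses will compare change between baseline and 16 weeks of mentoring in each of the above". PDQ-Carer gets its own sentence: "We will also compare change in PDQ-Carer between mid-study and Week 16 as an exploratory outcome". The next sentence says "we will run a series of repeated measures ANCOVAs for pre- and post- primary and secondary outcome measures", with no exception for PDQ-Carer. Those models are themselves called exploratory.

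The power paragraph in II.a gives the pilot's purpose as producing effect-size data and informing the sample size of a later randomized trial.

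**The concern.** A secondary outcome is normally measured before the intervention starts. PDQ-Carer is not, and it is the only mentee scale that III.d describes as measuring carer quality of life. A small change from mid-study to Week 16 could mean that mentoring did nothing for quality of life, or that the gain came before the first measurement. The data could not separate the two.

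The gap bears on the pilot's stated purpose. The plan can supply PDQ-Carer SDs at two times and a correlation over 6 to 8 weeks. It cannot supply the change over the full program, the SD of that change, or the correlation between a pre-intervention and a Week 16 score, which a later trial would need if it used this scale.

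The two tier labels add an ambiguity: whether the pre/post ANCOVAs include PDQ-Carer depends on which label the analyst follows. The point concerns mentees only.

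**Working it through.** The documents give no figure for the share of the program covered, so there is none to reproduce.

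**Program time covered.** Inputs from III.c: program length 16 weeks; first mentee PDQ-Carer at Week 8 or Week 10; second at the end of the program.

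Share covered = (16 − first week) / 16.

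| First PDQ-Carer | Elapsed | Covered by contrast |
|---|---|---|
| Week 8 | 8/16 = 50% | 8/16 = 50% |
| Week 10 | 10/16 = 62.5% | 6/16 = 37.5% |

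With weekly calls expected, about 8 or 10 of 16 would have taken place before the first score. If some mentees answer at Week 8 and others at Week 10, the average share lies between 37.5% and 50%; at an even split it is (50% + 37.5%) / 2 = 43.75%. The documents do not say which week applies to whom. Section V.g pays for an 8-week survey and mentions no 10-week one, which suggests Week 8 is usual but does not prove it.

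**Is a baseline simply unlisted?** The III.c list is introduced in open-ended terms. Section III.e makes an unlisted baseline unlikely: its baseline description names the same seven scales, and it gives PDQ-Carer a separate contrast that starts mid-study. So 7 of the 8 mentee outcome scales have a baseline and 1 does not.

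**Which tier governs the ANCOVA?**

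- Under Figure 3, PDQ-Carer is secondary. The ANCOVAs then include it, and no pre-intervention score exists. The mid-study score could be used as the first measure, but it is taken after 8 or 10 weeks of mentoring.
- Under III.e, PDQ-Carer is exploratory. The ANCOVAs, which cover primary and secondary measures, then leave it out and nothing is missing.

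The ANCOVA problem therefore exists only under the Figure 3 label.

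**Added burden of a baseline.** Item counts from III.d: mastery 7 + loneliness 3 + ZBI-12 12 + HADS 14 + GDS-SF 15 + DAS 20 = 71. The length of the knowledge test is not stated. Adding PDQ-Carer gives 71 + 29 = 100. The increase is 29/71 = 40.8%, an upper bound because the knowledge items are not counted. The Week 16 mentee survey already holds the same 100 countable items, plus falls and healthcare use.

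**The case against.** The strongest reply is that the plan hides nothing. Section III.e keeps PDQ-Carer out of the baseline comparisons, names both time points of its contrast and calls it exploratory. Carer quality of life is in none of H1 to H3. On this view, wanting a baseline for an exploratory scale is a design preference. That stands as to weight. It does not settle the label in Figure 3, and it does not give the pilot the missing quantities.

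A reader might infer that the ANCOVA gap is a second error. The documents do not support that: read in order, III.e calls PDQ-Carer exploratory and then plans ANCOVAs for primary and secondary measures only. The gap and the tier mismatch are one inconsistency.

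A reader might also infer that the contrast captures only 50% or 37.5% of the effect, or that power falls accordingly. The shares are of calendar time. The documents give neither the course of change over the 16 weeks nor an SD for PDQ-Carer, so no scaling of effect or power follows.

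On the remedy, two objections stand in part. Section V.g states no payment for the mentee baseline survey, while the Week 16 survey earns $75, so the longer baseline is a real, if small, imposition. The documents also do not say how many pairs have started. If many have, the 30 planned mentees would split into two groups with different contrasts, and the group with a baseline could be too small for a useful SD or correlation.

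**Conclusion.** The point holds and is minor. PDQ-Carer carries two tiers, mentees have no pre-intervention value for it, and the disclosed contrast covers the last 50% or 37.5% of program time. The pilot therefore cannot give whole-program change, its SD or the pre-post correlation for carer quality of life.

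This rests on reading the III.c baseline list as complete, which III.e supports, and on first measurement at Week 8 or Week 10 as written. No claim is made about how much of any change falls in the measured window. The study has no control arm, so even a baseline would give within-person change and not a causal effect of mentoring. H1 to H3 and the seven other mentee scales, which include burden, anxiety, depression and loneliness, are unaffected.

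**What to change.** 1. For mentees who have not started mentoring, add PDQ-Carer to the existing REDCap baseline survey, before the mentor's contact details are given. In III.e, make baseline to Week 16 their PDQ-Carer contrast, using the same paired t-test or Wilcoxon approach as for the other scales. Report mean change, SD of change and the pre-post correlation.
2. For mentees already started, report mid-study to Week 16 descriptively as late-program change only. Record the week each mentee answered, state the missing baseline as a limitation, and exclude these mentees from any PDQ-Carer pre/post ANCOVA.
3. Label PDQ-Carer exploratory in both Figure 3 and III.e, unless most mentees can still give a baseline.

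The cost is a short amendment and, for step 1, 29 more items at baseline: at most 41% more than the 71 countable now, in a survey with no stated payment. If no mentee can still give a baseline, only steps 2 and 3 apply. They add no questionnaire, only text changes and a record of the survey week.

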- Ι. Statistical analysis: The primary data will be entered into a HIPAA-compliant database (REDCap)⁴⁸, with quarterly audits for fidelity. Data will be exported to Stata 15 for analysis. Primary and secondary outcomes, covariates and confounders, and fidelity metrics are listed in Figure 2.
- II. Aim 1 (focus groups/interviews, PERSEVERE curriculum development): We will describe baseline demographics of focus group participants, transcribe recordings, and develop a theme codebook. Framework analysis⁴⁹ will be used to guide the revision of the structured, 16-week mentoring curriculum, with provision of practical checklists, goal setting, and step-by-step guides for key areas of LBD caregiving mastery in addition to social support. Several topics in the revised curriculum will be repeated or given two weeks to allow for reiteration in the event of missed mentoring calls.
- III. Aim 2 (peer mentor training, LBD caregiver mastery): We will describe the demographics, baseline mastery, LBD knowledge, and dementia attitudes of mentors pre-training, assessing for normality and reporting means/standard deviation or medians/interquartile range. We will compare within-subject change in mastery, LBD knowledge, and DAS pre- and post-training (primary outcomes) and pre-training and post-mentoring (secondary outcomes) using paired t-tests or Wilcoxon sign rank test, as appropriate.

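### Would adjusting the exploratory Aim 3 models for falls and healthcare use during mentoring distort the pre/post change?

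*Combined protocol and SAP*

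**What the plan says.** Section III.e, item IV (Aim 3) of the combined protocol and SAP has two layers.

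The first describes mentees at baseline, including "patient characteristics (including fall frequency and acute healthcare utilization", together with the outcome scales. It then states: "Bivariate analyses will compare change between baseline and 16 weeks of mentoring in each of the above". The tests are the paired t-test or the Wilcoxon signed-rank test, without covariates.

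The second layer is a set of adjusted models. Their purpose is given at the start: "To examine potential covariate effects, we will run a series of repeated measures ANCOVAs". Their content is "repeated measures ANCOVAs for pre- and post- primary and secondary outcome measures using demographic and confounder variables as nuisance variables", and their status is "These analyses will be considered exploratory due to the loss of degrees of freedom resulting from the covariates".

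The variables available for adjustment are in the last row of Figure 3 (end of section III.c). That row ties ADLs and IADLs to baseline. It also lists the patient's "monthly frequency of falls and acute healthcare utilization (combined" "number of ER visits not yielding admission + hospital nights) in the months prior to and", and the entry ends by naming the intervention period as well. Section III.e, item I says "Primary and secondary outcomes, covariates and confounders, and fidelity metrics are listed in Figure 2", but the only such list in the text is printed under Figure 3. That is a numbering slip and has no bearing on the analysis.

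**The concern.** A covariate measured after the intervention starts is not an ordinary nuisance variable. The introduction names fall prevention as a curriculum focus, and I.b (Background) describes education on causes of hospitalization. Mentoring might therefore reduce falls or admissions and improve caregiver outcomes partly by that route. Adjusting for the values during mentoring would then remove part of the change under study.

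The opposite is also possible. I.b says hospitalizations and caregiver strain grow as the disease progresses, so rising utilization could mask a benefit, and adjustment would raise the estimate.

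In either case a reader of an adjusted change could not tell whether it was the total pre/post change or the change net of falls and utilization. The stated caveat about degrees of freedom does not cover this. Section II.a says the pilot is meant to supply effect sizes for a larger randomized trial, so a mislabelled estimate could be carried forward. The path is more plausible for strain, anxiety and depression (secondary outcomes) than for mastery, LBD knowledge and loneliness (primary outcomes).

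**Working it through.** **Inputs.** From the plan: 30 mentees (II.a). The plan gives no covariate slope, SD of change, or expected shift in falls or utilization, and no adjusted estimate that could be reproduced. Every other number below is an assumption.

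**Formulas.** Let d be a mentee's post-minus-pre outcome, and x0 and x1 the covariate before and during mentoring.

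- Time-varying entry: d = δ + b(x1 − x0) + error, so adjusted change = mean(d) − b × mean(x1 − x0).
- Subject-level covariate z as a constant main effect: z takes the same value at both times and cancels in d, so adjusted change = mean(d).
- Mean-centred covariate of change: d = δ + c(z − mean z) + error. The least-squares intercept is exactly mean(d).

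Only the first form moves the change, and only if both b and the mean covariate change differ from zero.

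**First illustration.** Assumed: direct effect −0.20, b = 0.3, covariate SD 1, prior–during correlation 0.6, residual SD 0.7 at each time. Simulated values come from 4,000 replicates at n = 30.

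| Mean shift in falls | Unadjusted, formula | Simulated | Time-varying, formula | Simulated |
|---|---|---|---|---|
| −0.5 | −0.20 + 0.3 × (−0.5) = −0.35 | −0.350 | −0.35 + 0.15 = −0.20 | −0.199 |
| 0 | −0.20 | −0.199 | −0.20 | −0.199 |
| +0.5 | −0.20 + 0.3 × 0.5 = −0.05 | −0.047 | −0.05 − 0.15 = −0.20 | −0.196 |

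In the −0.5 case, the prior value alone or the value during mentoring alone as a constant main effect gave −0.350. Both together, mean-centred, also gave −0.350. Using the values during mentoring is therefore not enough to cause a shift.

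**Range.** The gap is slope × shift: 0.2 × 0.25 = 0.05 up to 0.4 × 0.5 = 0.20. The variance of change is b² × 2(1 − 0.6) + 2 × 0.7².

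- b = 0.2: 0.032 + 0.98 = 1.012; SE = √1.012/√30 = 0.184; 0.05/0.184 = 0.27.
- b = 0.4: 0.128 + 0.98 = 1.108; SE = √1.108/√30 = 0.192; 0.20/0.192 = 1.04.

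**Second illustration, other assumptions.** Raw change +2.0, residual SD of change 3.5, SD of covariate change 1.

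- b = −1: a shift of −1 gives 2 − 1 = 1.0 (simulated 0.98); a shift of +1 gives 2 + 1 = 3.0 (3.01).
- b = 0.5: a shift of −1 gives 2.5 (2.50); a shift of +1 gives 1.5 (1.51).
- Mean-centred entry stayed at 1.99 to 2.02 throughout.

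**What the plan would have to say for harm to follow.** All five of these must hold:

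1. The values during mentoring are among the variables entered. Figure 3's row pools demographics, confounders and covariates; III.e names demographics and confounders and lists none.
2. They enter as time-varying. Nothing says so.
3. Their mean changes over 16 weeks. Not known.
4. Their slope on the outcome is non-zero. Not known.
5. The adjusted change is reported as mentoring's effect. No passage says this; the stated purpose is to look at covariate effects.

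**The case for a change.** The best case for a change is as follows. The covariate has a before and a during value, just as the outcome has a pre and a post value, so pairing them is a natural repeated-measures layout. In the same row ADLs and IADLs are limited to baseline, so the later values for falls and utilization look deliberate. Read literally, III.e both tests the change in these variables and makes them available as nuisance variables. One clarifying sentence would cost almost nothing.

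Much of this stands. Time-varying entry is a realistic reading, the double role is real, and the degrees-of-freedom caveat does not warn of a different estimand. But it shows an unspecified exploratory model, not a wrong one.

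Restricting the models to mean-centred, pre-mentoring covariates would also gain little, because by the third formula the adjusted change then equals the raw mean change already reported from the paired analysis. Nor is that restriction clearly better. With a single arm, neither the raw nor the adjusted change isolates mentoring, and values during mentoring may reflect mediation or progression. In the progression row of the table, adjustment recovers the assumed −0.20 while the raw change shows −0.05.

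One further point concerns centring. An uncentred subject-level covariate of change makes the intercept the change at zero falls. That happens with prior values as much as with later ones, so it is a general modelling matter and not a fault of this covariate list.

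**Conclusion.** No change to the plan follows. The observation about the text is correct: falls and utilization during mentoring are in the covariate row, and III.e does not exclude them. The algebra is correct for time-varying entry. The effect is zero under the other forms examined, assuming complete pre/post pairs.

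The possible gap of 0.05 to 0.20 (0.3 to 1.0 standard errors) rests entirely on assumed slopes, shifts and SDs. It shows how the mechanism works and is not a forecast for this trial.

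The Aim 3 conclusions rest on paired tests that use no covariates. The ANCOVAs are labelled exploratory, and relating outcome change to falls or utilization during mentoring fits their stated purpose. Whoever fits them must choose the variables and their form, and ordinary reporting would state that choice and describe any time-varying result as net of falls and utilization. Which version is preferable is a choice of estimand on which statisticians may fairly differ.
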